4.0 Expected Outcome

Table 2: Angular and Linear Measurement of Cephalometric Values

Measurements	AI-based (WeDoCeph)			Manual			P-value
	Mean	S.D	r²	Mean	S.D	r²	
SNA (°)	n	n	n	n	n	n	n
SNB (°)	n	n	n	n	n	n	n
ANB (°)	n	n	n	n	n	n	n
FMPA (°)	n	n	n	n	n	n	n
MMPA (°)	n	n	n	n	n	n	n
UIA (°)	n	n	n	n	n	n	n
LIA (°)	n	n	n	n	n	n	n
IIA (°)	n	n	n	n	n	n	n
A-N perpendicular (mm)	n	n	n	n	n	n	n
POG-N perpendicular (mm)	n	n	n	n	n	n	n
ANS-Me perpendicular (mm)	n	n	n	n	n	n	n
SN (mm)	n	n	n	n	n	n	n
LFH (mm)	n	n	n	n	n	n	n
UFH (mm)	n	n	n	n	n	n	n
MxPI (mm)	n	n	n	n	n	n	n
MnPI (mm)	n	n	n	n	n	n	n

Table 3: Intraclass Correlation Coefficient

Intraclass Correlation	95% Confidence Interval			F Test with True Value 0			
	Lower Bound	Upper Bound	Value	df1	df2	sig	
Single Measures							
Average Measures							

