3.0 Materials and Methods

3.1 Study Population

This prospective study includes 40 cephalometric radiographs of orthodontic patients seen in Orthodontic Specialist Clinic of Kulliyyah of Dentistry, IIUM Kuantan.

The sample size calculation was done with a significance level of 0.05 and a power value of 95%. A sample of a minimum of 37 radiographs was needed.

3.2 Inclusion criteria:

- Pretreatment OR post-treatment lateral cephalometric radiographs
- Orthodontic patients treated at the Orthodontic Specialist Clinic, IIUM
- Radiographs obtained between January 2023 and June 2023
- High-quality cephalograms without flaws affecting anatomical landmark positions

3.3 Exclusion criteria:

- Patients with surgical rigid fixations visible on radiographs
- Presence of orthodontic appliances on radiographs
- Presence of dental prostheses on radiographs
- Patients with syndromes and craniofacial deformities.

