3.4 Methodology

Ethical approval will be obtained before the commencement of the study. Forty cephalometric radiographs will be selected. Calibration will be done prior to landmark identification to ensure agreement between the examiners.

For manual tracing, 18cm x 24cm of radiographic film images of lateral cephalograms will be obtained and traced manually on a view box using transilluminated light under dark room. Each cephalograms will be secured over the view box first, and then a sheet of matte acetate tracing paper sized 22cm x 28cm are taped over the radiographic film. Three orientation marks will be placed as a reference point over the film and the tracing paper. After that, hard and tissue landmarks will be traced onto the tracing paper manually using a HB pencil. A total of 11 anatomical landmarks will be plotted on each cephalograms which are the A point (subspinale, or A), B point (B), sella (S), nasion (N), orbitale (O), porion (Po), anterior nasal spine (ANS), posterior nasal spine (PNS), gonion (Go), menton (Me) and pogonion (Pog).

Measurements of the cephalometric parameters (8 angular and 8 linear) will be taken with the help of millimetre ruler and a protractor. All measurements will be performed twice by the same investigator with intervals of 4 weeks from the first measurements. Angular measurements ($^{\circ}$) include the SNA, SNB, ANB, FMPA, MMPA, UIA, LIA, IIA. While the linear measurements (mm) include the NA, NPog, ANS-Me, SN, LFH, UFH, MxPI, MnPI.

Table 1: Definition of the relevant cephalometric points

Cephalometric points	Definition
Point A (A)	The deepest point in the concavity of the anterior maxilla between the ANS and alveolar crest
Point B (B)	The deepest point in the concavity of the anterior mandible between the alveolar crest and Pog
Sella (S)	The midpoint of sella turcica
Nasion (N)	Junction of the frontal and nasal bones at the frontonasal suture
Orbitale (O)	The most inferior point on the infra- orbital margin
Porion (Po)	The most superior point of the external auditory meatus
Anterior Nasal Spine (ANS)	The anterior limit of the nasal floor
Posterior Nasal Spine (PNS)	The posterior limit of the nasal floor
Gonion (Go)	The most posterior and inferior point on the angle of the mandible
Menton (Me)	The most inferior point on the bony chin
Pogonion (Pog)	The most anterior point on the bony chin

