3.5 Data Analysis

The mean, standard deviation, and standard error of the difference between the repeated measurements for each method and between the two methods will be calculated. The reliability of each method will be defined using the Pearson correlation coefficient (r^2). The level of statistical significance will be set at $P < 0.05$.

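### Table 3 tests the ICC only against zero, which cannot show adequate repeatability, and the plan sets no minimum ICC and does not say which ICC row applies

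*Combined protocol and SAP*

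**What the plan says.** Section 4.0, Table 3 is an empty ICC template. It has a single-measures row and a second row headed "Average Measures". Its columns hold the "95% Confidence Interval" and an "F Test with True Value 0" with two degrees of freedom and a significance value. The table does not name a method, a parameter or the comparison it covers.

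Section 3.5 does not mention an ICC. It defines the reliability of each method by the Pearson coefficient, written as r², and it also plans the mean, SD and standard error of the difference between repeated measurements. It ends with a general level: "The level of statistical significance will be set at" P < 0.05.

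On the number of films, section 3.1 says "This prospective study includes 40 cephalometric radiographs". On repeats, section 3.4 says of manual tracing that "All measurements will be performed twice by the same investigator with intervals of 4 weeks from the first measurements", and describes a second AI run after the same interval. Sections 1.3 and 1.4.2 frame reliability as a comparison: the hypothesis is that AI is more reliable than manual tracing.

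No section gives a minimum acceptable ICC or r², an ICC model, or the row on which a conclusion would rest.

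**The concern.** Two readings of the same film by the same person should correlate even when the reading is poor, because films differ from one another. Rejecting an ICC of zero therefore shows only that the readings are not pure noise. What a clinician needs to know is whether the reading error is small enough, and a null of zero does not address that.

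The second row adds a choice. An average-measures ICC describes the mean of two readings. Nothing in section 3.4 says that two readings will be averaged, so the single-measures row looks like the relevant one. The plan leaves the choice open, and the average row is the larger whenever the single-measures ICC lies between 0 and 1.

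At stake is objective 2. With no minimum fixed in advance, a modest ICC can be presented with a very small P value beside it. Nor would two such tests, one per method, answer whether AI is the more reliable.

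**Working it through.** **The plan's own figure.** The documents compute nothing for the ICC. The one computed figure is in section 3.1: "A sample of a minimum of 37 radiographs was needed", from "a significance level of 0.05 and a power value of 95"%. No test, effect size or SD is given, so 37 cannot be reproduced. It is not used below, except to show that the threshold hardly moves.

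**Inputs.** n = 40 films (3.1); k = 2 readings per method (3.4); level 0.05 (3.5); null ICC = 0 (Table 3). Assumption: Table 3 covers the two repeat readings of one method. The ICC model is not stated, so two were tried.

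**Smallest ICC that reaches significance.** With k = 2, single-measures ICC = (F − 1)/(F + 1).
- Two-way consistency, 39 and 39 df: critical F = 1.704, so ICC = 0.704/2.704 = 0.26.
- One-way, 39 and 40 df: critical F = 1.697, so ICC = 0.697/2.697 = 0.26.
- With 37 films the threshold is 0.27 under either model.

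**Chance of significance at a true ICC of ρ.** P[F(39,39) > 1.704 × (1 − ρ)/(1 + ρ)]:

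| True ICC | 0.2 | 0.3 | 0.4 | 0.5 | 0.6 |
|---|---|---|---|---|---|
| P(significant) | 0.35 | 0.60 | 0.83 | 0.96 | 0.995 |

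**What an ICC of 0.5 means in units.** Error SD = √(1 − ICC) × total SD = 0.71 × total SD, and 95% of repeat differences lie within 1.96 × √2 = 2.77 error SDs. The documents give no total SD, so a range is assumed:

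| Assumed total SD | Error SD | 95% of repeat differences within |
|---|---|---|
| 3° | 2.1° | 5.9° |
| 4° | 2.8° | 7.8° |
| 6° | 4.2° | 11.8° |

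**Average row.** Average ICC = 2 × ICC/(1 + ICC). So 0.60 becomes 1.20/1.60 = 0.75, and 0.75 becomes 1.50/1.75 = 0.86. Under the usual models both rows come from the same F and share one P value.

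**What a non-zero minimum would require.** Take 0.75 purely as an example. A lower 95% limit of 0.75 corresponds to F = (1 + 0.75)/(1 − 0.75) = 7 after division by F(0.975; 39,39) = 1.891. The observed F must therefore be 7 × 1.891 = 13.2, giving an ICC of 12.2/14.2 = 0.86. A true ICC of 0.9 would meet this rule with probability 0.87, and a true ICC of 0.5 almost never (about 0.000005). These limits use the consistency form; an absolute-agreement ICC will be somewhat lower if there is a shift between sessions.

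**The case against.** The strongest reply is that no sentence makes this P value the reliability verdict. Section 3.5 rests reliability on r², and Table 2 attaches no P value to r². That is correct. A reader might infer that any method significant in Table 3 would be declared reliable, or that r² will be tested against zero in the same way; the documents state neither rule.

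It can also be said that the plan already shows what is needed to spot poor repeatability. Table 3 has the single-measures ICC with its interval. At an observed ICC of 0.50 the reader would see P = 0.0004 but also an interval of 0.23 to 0.70. At an observed 0.264 (P = 0.048) the two-sided interval runs from −0.05 to 0.53. Section 3.5 also plans the SD of repeat differences, which is in degrees or mm. This stands too, so it would be wrong to conclude that the reliability results carry no information.

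The average row does not make a poor method significant, since it shares the P value; it only enlarges the coefficient. Nor does nearly any result pass: at a true ICC of 0.2 the chance is 0.35.

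Finally, Table 3 might concern agreement between examiners, since section 3.4 mentions calibrating them. The documents do not settle this, which is why the calculation is conditional.

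None of these replies supplies a minimum ICC, a deciding row, or a reason to test against zero.

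**Conclusion.** The point holds as a limited one. The only significance test laid out for the ICC has a null that is uninformative about adequate repeatability, and the plan fixes neither a minimum ICC nor the row that applies. The threshold of 0.26 and the probabilities in the table assume 40 films, two readings, a level of 0.05, and that Table 3 covers the repeat readings. They would not carry over to examiner calibration, for which no number of films or examiners is given. The figures in degrees depend on the assumed total SD.

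The documents do not support the stronger conclusion that a badly repeating method would be reported as reliable. They contain no such decision rule, and other planned output would show the problem. The gap is that adequacy is left to be judged after the results are seen, and that the comparison of reliability in the hypothesis has no analysis in this table.

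**What to change.** In Table 3, remove the F test against zero and the average-measures row. State the comparison covered, and give one row per parameter and method with the single-measures, absolute-agreement ICC and its 95% interval. In section 3.5, name that ICC model and say that a parameter is called reliable only if the lower limit exceeds a minimum fixed before any film is read. The investigators must choose and justify that minimum; 0.75 is only an example.

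Beside the ICC, report each method's within-film SD (the planned SD of the repeat difference divided by √2) and 2.77 times that value, in degrees or mm. Keep the planned mean difference next to it, because the SD does not show a shift between sessions. Then compare the within-film SDs of AI and manual for each parameter, with an interval that respects the fact that both methods read the same films. This comparison is needed because a pass mark applied to each method separately does not test whether AI is more reliable.

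The cost is a new table layout and a few sentences in section 3.5, using readings already planned. The downside is that some parameters may no longer be called reliable.

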5.0 Gantt Chart

Project Activities	2022		2023												2024		
Months	NOV	DEC	JAN	FEB	MAR	APR	MAY	JUN	JUL	AUG	SEP	OCT	NOV	DEC	JAN	FEB	
Distribution of research titles																	
Literature review & proposal preparation																	
Proposal presentation																	
Hand-in written proposal																	
Ethical Approval																	
Data collection																	
Data analysis																	
Final research writing																	
Complete report submission																	
Draft for publication																	

Presentation at
DSSC

